Participant Discontinuation/Withdrawal: Because the study intervention is a health systems practice facilitation rather than a specific patient intervention, we do not anticipate that participants will discontinue the study intervention, but remain in the study for follow-up. That said, participants may withdraw voluntarily from the study or study investigators (PIs) may discontinue a participant from the study. Adverse events that will result in withdrawal of participants from the study include development of complications of hypertension and serious adverse events as determined by the DSMB. All cases of study discontinuation and participant discontinuation/withdrawal from the study will be documented separately in electronic formats. In addition, a dedicated Case Report Form (CRF) page will be used to capture the date and the specific underlying reason for discontinuation of study intervention or participant discontinuation/withdrawal.

SECTION 5: Training, Monitoring, Quality Control and Assurance

Training of the HIV nurses and Practice Outreach Facilitators . See section 7 above. In addition, the study staff in Nigeria will receive ongoing training on the appropriate execution of the study protocol.

Study monitoring and quality control will be provided as follows.

Training of the study team, HIV nurses and POFs will be overseen by the principal investigators.

Oversight of study protocol will be monitored by an independent Data Safety Management Board (DSMB), which will be formed to monitor the safety of the study subjects, the validity and integrity of the study activities, as well as the data from the study. The general responsibilities of the DSMB are to:

Review the research protocol and plans for data and safety monitoring.

Evaluate the progress of the study, including periodic assessments of data quality and timeliness, participant recruitment, accrual and retention, participant risk versus benefit, performance of trial sites, and other factors that can affect study outcome.

Monitor external factors to the study when interpreting the data, such as scientific or therapeutic developments that may have an impact on the safety of the participants or the ethics of the study. For example, a systematic trend showing poorer, rather than increased, BP control or cardiovascular risk profile, in the intervention vs. the control condition.

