Follow-up Study Visits (6, 12, 18, and 24 months): The research coordinator (RC) will meet with each patient to collect follow up data on primary outcome measure (BP measurements identical to that described for the baseline visit) and secondary outcomes. Study measures for both groups are similar and will be conducted in the same manner by the RC. Patients in the HIV clinics randomized to the Self-Directed Group will attend follow up study visits as scheduled while those in the clinics randomized to the PF Intervention will meet with their nurses every three months [for lifestyle counseling and treatment] in addition to the scheduled study visits.

On-time Follow-up Study Visits (6, 12, 18, and 24 months): On-time visit occurs within a +/- 3-months window of the expected follow-up date. For the 6-month follow-up visit, an on-time visit occurs between 3 and 9 months after baseline visit. For the 12-month visit, an on-time visit occurs between 9 and 15 months. For the 18-month visit, an on-time visit occurs between 15 and 21 months.

Baseline visits: The RC will confirm eligibility status and obtain informed consent from each patient. At baseline, we will measure the organizational and individual-level factors shown to affect implementation of evidence-based practices, including leadership, organizational capacity to change, individual attitudes toward evidence-based practices, and the degree of buy-in among practice facilitators.

SECTION 6: Study Measures

Primary Outcome: Change in systolic BP from baseline to 12 months. The SBP reduction in patients will be assessed as mean change in systolic BP from baseline to 12 months.

Secondary Outcomes are:

Adoption [proportion of patients who were correctly diagnosed with HTN, received lifestyle counseling and antihypertensive treatment]; and *sustainability* [maintenance of TASSH uptake at the HIV clinics at 24 months].

The mediators of TASSH across the HIV clinics at 12 and 24 months.

Assessment of Outcome Measures:

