determined. A detailed analysis of the interviews should generate a conceptual model that elucidates barriers and facilitators of the uptake of TASSH within participating HIV clinics in Nigeria. It should also suggest modified facilitation strategies tailored to the clinics' context to overcome these challenges.

Analysis for Aim 2

Analysis for Aim 2 will consist of a repeated measures mixed-effects model for systolic BP (SBP), with fixed effects for time and intervention arm, and random effects for clinic. An interaction term be included for the intervention arm and time; this interaction, if non-zero, will indicate that the degree of change of SBP over time differs for those in the practice facilitation intervention compared to those in the self-directed condition. Also, for this aim assessments will include whether adjustment for any baseline characteristics is necessary, including such adjustments based on the change-in-estimate criteria.

Analysis for Aim 3

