This aim will assess the extent to which inner setting variables (e.g., implementation leadership, implementation climate, and organizational culture) affect the degree of adoption of TASSH as defined in Aim 3, and its sustainability at 24 months. Particular attention will be paid to the pathways via which this occurs. We will estimate a just-identified path model using the robust weighted least squares estimator to investigate relationships among the theoretical mediators of implementation climate, implementation leadership, organizational culture, organizational readiness to change, and external change agent support. Based on our conceptual model, we will test the direct effects from the theoretical constructs to the adoption components (individually). In addition to the direct effects, the indirect effects from each variable to adoption via inner setting variables will be estimated as the product of component direct effects and tested using bootstrapped 95% confidence intervals. Finally, we will estimate the direct effects of the

predicted model of adoption on SBP reduction. Predicted probabilities of the adoption and sustainability outcomes and SBP will be calculated from path model coefficients to elucidate the magnitudes of direct and indirect effects.

Methods for handling missing data:

Although we will attempt to retain as high a fraction of participants as possible, we acknowledge that some attrition is likely, leading to missing outcome values. The generalized linear mixed models proposed for the primary and secondary analyses incorporate an assumption of data that are missing at random (MAR), meaning that the likelihood of a value being missing depends on observable characteristics (e.g., sex or age). In sensitivity analyses, we will assess the impact of different assumptions about the missing data mechanism, and will determine the robustness of trial results to these different assumptions. We will consider the use of multiple imputations of missing data as an alternative sensitivity analysis.

SECTION 7: Ethical Consideration

Institutional Review Board Approvals for this study will be obtained from the NYU School of Medicine (NYU) and the Nigerian Institute of Medical Research (NIMR).

Informed consent

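### Withdrawing patients from the study for hypertension complications or DSMB-determined SAEs leaves outcome-related gaps in 12-month SBP and makes MAR doubtful

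*Combined protocol and SAP*

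**What the plan says.** **Withdrawal rule.** Section 4 (Participant Discontinuation/Withdrawal) says: "Adverse events that will result in withdrawal of participants from the study include development of complications of hypertension and serious adverse events". The sentence closes with a qualifier that refers to a determination by the DSMB. The wording leaves open whether that qualifier covers both triggers or only the SAEs. The same paragraph says of the alternative, stopping the intervention while staying under observation: "we do not anticipate that participants will discontinue the study intervention, but remain in the study for follow-up". It also provides that "a dedicated Case Report Form (CRF) page will be used to capture the date and the specific underlying reason for discontinuation" or withdrawal. Nothing describes BP collection after withdrawal. The adverse-event text in Section 6 follows the event to its outcome but does not mention SBP.

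**Outcome and model.** Section 6 defines "Primary Outcome: Change in systolic BP from baseline to 12 months". Analysis for Aim 2 specifies a "repeated measures mixed-effects model for systolic BP (SBP), with fixed effects for time and intervention arm, and random effects for clinic", plus an arm-by-time interaction. It names no patient-level random effect or within-patient covariance.

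**Missing data.** Methods for handling missing data says that the mixed models "incorporate an assumption of data that are missing at random (MAR") and gives sex and age as examples of the characteristics on which missingness may depend. It promises sensitivity analyses under other assumptions about the mechanism, without naming a method, scenario or parameter. Multiple imputation is only to be considered.

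**Contact by arm.** Study visits are the same in both arms. Under Follow-up Study Visits, patients in practice facilitation (PF) clinics also "will meet with their nurses every three months".

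**The concern.** A complication of hypertension is a consequence of poor BP control, and BP control is what the trial measures. A rule that ends study participation at such an event tends to remove the 12-month readings of patients who are doing badly. An analysis that treats those readings as missing at random may then represent these patients by values that are too low.

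The error matters for the arm comparison only if it differs between arms, and there are two routes to that. If PF lowers SBP, fewer PF patients may have complications. The self-directed arm then loses more high readings and the effect is diluted. If the extra nurse contacts in PF clinics bring more complications to light, the PF arm loses more high readings and the effect is exaggerated. HIV nurses, whose practice the intervention targets, also assess adverse events, and patients and coordinators are not blinded. Equal losses therefore cannot be taken for granted. A larger sample does not correct an error of this kind.

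**Working it through.** The plan gives no figure to reproduce on this point. The protocol text gives no withdrawal rate, complication rate, SD, ICC or target difference. Everything below except the number of clinics and patients is therefore an assumption.

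**Inputs from the documents.** 30 clinics (15 per arm) and about 32 patients per clinic: 30 × 32 = 960 patients, 15 × 32 = 480 per arm.

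**Step 1: size of the bias.** Let p be the proportion withdrawn in an arm. Let d be the mean true 12-month SBP of its withdrawn patients minus what the model implies for them. The model understates that arm's mean by p × d, so

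bias in (PF − self-directed) = p(self-directed) × d(self-directed) − p(PF) × d(PF).

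A positive value moves the result towards no effect when PF lowers SBP. With the same d in both arms:

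| Self-directed / PF withdrawn | d = 10 mmHg | d = 20 mmHg |
|---|---|---|
| equal rates | 0 | 0 |
| 1 point more in self-directed | +0.1 | +0.2 |
| 5% / 3% | +0.2 | +0.4 |
| 10% / 5% | +0.5 | +1.0 |
| 5% / 10% | −0.5 | −1.0 |

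A 5-point difference corresponds to 0.05 × 480 = 24 patients.

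**Step 2: what the model can recover.** A large simulation (2,000,000 patients per arm) used SBP at 0, 6 and 12 months, SD 16, within-patient correlation 0.5, a true effect of −5 mmHg unless stated, withdrawal after month 6 and no clinic effect. It compares using observed 12-month means only (no within-patient covariance) with predicting from the patient's own earlier SBP. Bias in mmHg:

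| Withdrawal driven by | Withdrawn, self-directed / PF | No within-patient covariance | With it |
|---|---|---|---|
| 6-month SBP, same rule in both arms | 5.0% / 4.4% | +0.04 | 0.00 |
| 6-month SBP, PF detection doubled | 5.0% / 8.7% | −0.31 | 0.00 |
| 12-month SBP, same rule | 5.0% / 3.8% | +0.16 | +0.11 |
| 12-month SBP, same rule | 10.0% / 7.8% | +0.30 | +0.20 |
| 12-month SBP, PF detection doubled | 5.0% / 7.6% | −0.44 | −0.30 |
| 12-month SBP, PF detection doubled, no true effect | 5.0% / 10.0% | −0.80 | −0.55 |

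When observed SBP explains withdrawal and within-patient covariance is modelled, the bias vanishes. When the unobserved 12-month value drives withdrawal, neither structure removes it.

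**Step 3: scale.** Detectable difference at 80% power, assuming two-sided alpha 0.05:

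SD × √(2 × [1 + 31 × ICC] / 480) × (1.96 + 0.84).

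- SD 14, ICC 0.01: design effect 1.31, giving 2.9 mmHg.
- SD 20, ICC 0.05: design effect 2.55, giving 5.8 mmHg.

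The largest bias in Step 1 is thus between 1.0/5.8 = 17% and 1.0/2.9 = 34% of a detectable difference.

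**The case against.** **The rule is narrower than it may look.** A reader might infer that every SAE removes a patient, and does so because of SBP. The text does not support that. At least for SAEs, withdrawal rests on a DSMB determination, and SAEs include deaths and hospital stays of any cause. This limits how many patients are affected. It does not keep BP being measured in those who are withdrawn.

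**Sensitivity analyses are planned.** A reader might also infer that the plan relies on MAR alone. It does not: robustness to other mechanisms is promised, and the CRF records the reason for withdrawal, which is what a reason-specific analysis needs. What is missing is the specification. No sensitivity analysis can restore readings that were never taken.

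**Bias is not proven.** Sex and age are only examples, and a repeated-measures model can draw on baseline and 6-month SBP. This stands, with the reservation that Aim 2 names only a clinic random effect.

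**The size may be flattering.** The gap that counts is the part the model does not predict. With two earlier readings correlated at 0.5, R² = 2 × 0.25 / 1.5 = 1/3. If 10 to 20 mmHg were instead the raw gap, and the 12-month value drove withdrawal, the range would shrink by a factor of 2/3 to about 0.07 to 0.67 mmHg. Eligibility also excludes stroke, heart disease, kidney disease, diabetes and BP above 180/110, so a 5-point arm difference within a year is not obviously likely.

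**Differential detection is conjecture.** Adverse events are assessed at study visits common to both arms, and nothing says the extra PF contacts trigger withdrawals. It remains a possibility that the plan does not rule out.

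**Conclusion.** The concern holds in a limited form. Followed as written, the plan will lose some 12-month SBP values for reasons related to the primary outcome. That makes MAR doubtful and may bias the comparison towards or away from an effect of PF. The rule, and the absence of any provision for BP measurement afterwards, are clear from the text. The size is not. Under assumed arm differences of 1 to 5 percentage points and gaps of 10 to 20 mmHg beyond the model's prediction, it is about 0.1 to 1.0 mmHg. It is near zero under equal rates and gaps, or where earlier SBP explains withdrawal and within-patient covariance is modelled.

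The stronger conclusion, that the primary analysis is biased and the mixed model cannot recover the loss, does not follow. Outcome-related withdrawal casts doubt on MAR but does not establish that data are missing not at random, and the documents give no rates from which to show a difference between arms. The case for acting is that the loss is avoidable at little cost and cannot be repaired once the 12-month visit has passed.

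**What to change.** Amend the Section 4 paragraph to separate stopping the intervention, or a change in care, from stopping data collection. For example: *A complication of hypertension or an SAE does not by itself end data collection. The research coordinator will still seek the scheduled BP readings, at least at 12 months, where the participant's consent continues and neither the DSMB nor the investigator has ruled out further contact.* DSMB and investigator authority, and the clinical handling of these patients, stay as they are.

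In the statistical section:

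- Analyse all SBP obtained by randomised arm, whatever events occurred.
- Report deaths separately, since no 12-month SBP exists for them.
- Make one of the promised sensitivity analyses a prespecified delta-adjusted analysis by arm and withdrawal reason, using the reason on the CRF page.

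The cost is a short amendment, a few extra follow-up visits within a schedule the coordinators already run, and a little more analysis. For patients whose readings are obtained, this source of bias disappears. The delta-adjusted analysis covers those who still cannot be measured.

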The practice facilitation intervention has three components, which are all described below along with the mode of delivery.

Formation of the advisory board to guide PF intervention: Advisory board members will be constituted from the Steering Committee members. It will comprise leaders from the Directorate of Nursing, physicians, HIV clinic nurses, leaders from the Lagos State Primary Healthcare Board (LSPHB), leaders from the Lagos State AIDS Control Agency, and patient advocates.

Development of the practice facilitation strategy. Components of the PF strategy are described below.

Training of the POFs using a train-the-trainer model: After randomization and recruitment of POFs, we will start the intervention with a “kick off” learning session, where we will review components of the TASSH protocol; quality improvement methods; the study timeline and evaluation plan with the POFs. Additionally, the POFs will be training to coach the HIV nurses on *Engaging*, *Enhancing*, and *Evaluating* their tasks as part of this intervention. POFs will carry out this function via onsite and remote supportive supervision of the HIV nurses. The basis of the strategy is to *Engage* the HIV nurses (via monthly phone calls to address barriers that the HIV nurses may have in performing their duties), *Enhance* the HIV nurses (via onsite visits quarterly to observe and supervise them in their duties) and *Evaluate* the HIV nurses (via onsite supervision and use of learning communities). Study staff will certify and re-certify the POFs as trainers yearly using a train-the-trainer model.

Identify site champion and coordinator: To ensure buy-in, each PHC is required to identify a site champion and coordinator (the POFs) who will serve as the implementation team. Site leadership is also required to sign a memorandum of agreement that describes all project activities in which staff are required to participate.

Build consensus for quality improvement targets: Onsite meetings with the POFs will occur bi-weekly for the first month and then monthly thereafter to facilitate practice changes to support the implementation of TASSH at the PHC. At the first onsite meeting, the HIV nurses will review baseline data on the proportion of their patients with HTN, review the TASSH protocol, and set targets for the PHCs.

Implement practice changes to support TASSH implementation: This activity will be conducted accordingly:

Assessment of participant screening practices.

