Blood pressure measurements: At baseline, three BP readings will be taken by trained research coordinator using an automated BP monitor with participant seated comfortably for 5 minutes prior to the measurements, following standard guideline. The average of three BP readings will be used as the measure for each visit. The same procedure will be followed at the 6, 12-month study visit. Uncontrolled BP is defined as average clinic systolic BP>140 mmHg or diastolic BP>90 mmHg following the guidelines set forth by WHO for CVD treatment²⁸ and in accordance to the Nigerian healthcare policy.

Rate of adoption of TASSH is defined as the proportion of patients who were diagnosed with HTN by the HIV nurses; received lifestyle counseling and antihypertensive treatment from HIV nurses. For this purpose, adoption will be assessed by the following measures: 1) the number of hypertensive patients diagnosed by

the nurses using the WHO CVD risk assessment; 2) proportion of patients with HTN who received lifestyle counseling from the nurses; and 3) proportion of patients for whom the HIV nurses initiated treatment with antihypertensive medications. In order to assess this measure, the nurses will complete a questionnaire inquiring about the number of patients with uncontrolled HTN who received medication treatment and lifestyle counseling. For this purpose, all nurses will be required to keep an attendance log sheet for their patients' visits.

Sustainability of TASSH is defined as the maintenance of TASSH adoption at the HIV clinics at 24 months (one year after the end of the intervention). Sustainability will be assessed with a quantitative rate similar to adoption (as defined above) and qualitatively, based on interviews with nurses and clinic leadership at 24 months. The research coordinator will conduct the interviews with two nurses, and one key leadership personnel at each clinic. The interviews will be guided by CFIR and inquire about attitudes regarding the implementation of TASSH, barriers, facilitators, and implications for scalability. All interviews will be recorded, transcribed and analyzed with NVIVO Version 11.

The mediators of TASSH will be assessed via self-report. The mediators are based on the constructs of the CFIR framework including inner setting characteristics of the clinics, intervention characteristics, and implementation process measures as outlined below.

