For adoption, the analysis will have one within person factor – Time (baseline and 12-month coded naturally as months [0 and 12]) – and one primary between-patient factor – (Randomization Group dummy coded as 0 = Self-directed Condition and 1 = Practice Facilitation). Fixed effects will be specified for time, randomization group and their interaction effect (group by time). The outcome measure will be a composite index for adoption of TASSH (defined as patients diagnosed with HTN, received lifestyle counseling and treatment for HTN by the HIV nurses). Additionally, the nurses will be nested within clinics creating a 3-level analytic model (observations nested within nurses nested within clinics). Random effects will be specified for clinics and for nurses, adjusting for the clustering of measures within nurse and nurses within clinic. Multilevel modeling software (SAS, Version 9, PROC MIXED) will be used to compute full information maximum likelihood (FIML) estimates of the model parameters. The PROC MIXED procedure will use an error structure that allows for the possibility of group differences in (a) the error variances at 12 months; and (b) the serial correlations of the baseline with the 12-month outcomes. For sustainability, the analysis will be repeated as described above but will be evaluated at 24 months instead of 12 months. Adoption at 12 months will be assessed using questionnaires completed by nurses and sustainability at 24 months will be assessed with site interviews and site visits. Levels of adoption and sustainability will be compared between the group that randomized to the PF intervention and the group randomized to the self-directed condition. The qualitative components of sustainability at 24 months will be assessed using interviews with nurses and clinic leadership. These interviews will be recorded, transcribed and entered into NVIVO Version 11 for analysis. The analytic plan will be similar to the qualitative methods described for Aim 1.

Analysis for Aim 4

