Potential value of the study: The intervention will benefit the participants by improving their blood pressure control, reducing their cardiovascular risk profile, and increasing their role as active participants in the management of their HTN. The ultimate aim is to develop a facilitation strategy that can be delivered nationally at little expense; thus, the benefit to others will occur when the intervention becomes a routine part of activities at the PHCs. Overall, the benefits of understanding effective methods for helping vulnerable populations, i.e. people living with HIV (PWH), reduce their cardiovascular risk far outweigh the remote possibility of a breach of confidentiality. The study may also have relevance to

other PHCs by testing new strategies to enhance implementation of evidence-based interventions for improving hypertension control in high-risk populations

SECTION 9 :Timeline

TIMELINE AND MILESTONES	YEAR 1				YEAR 2				YEAR 3				YEAR 4				YEAR 5			
	3	6	9	12	15	18	21	24	27	30	33	36	39	42	45	48	51	54	57	60
Start up																				
Convene collaborative kickoff with project partners and subsequent weekly subcommittee meetings																				
Define roles and responsibilities of SC and establish meeting schedule																				
Establish DSMB																				
Announce project kickoff broadly/launch site recruitment and retention plan																				
Hire/train research and program staff																				
IRB application submitted/approved																				
Develop project website																				
Establish study databases, finalize baseline assessment survey and fidelity tracking tools (survey/non-clinical measures)																				
Complete practice facilitator training																				
Pre-implementation Phase																				
Conduct key informant interviews																				
Refine and finalize facilitation/intervention materials and protocols with participation of the Steering Committee																				
Implementation Phase (Intervention Period)																				
Baseline assessments of primary and secondary outcomes																				
Randomization of HIV clinics																				
Site retention activities																				
Post-Implementation Phase																				
Conduct interviews and site visits																				
Extract utilization and referral data from health record																				
Evaluation																				

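### Adoption is scored from unchecked questionnaires filled in by the nurses who deliver TASSH and know their arm, and the protocol contradicts itself on the source and composite for sustainability at 24 months.

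*Combined protocol and SAP*

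**What the plan says.** **Source at 12 months.** Section 6 (Assessment of Outcome Measures) states that "the nurses will complete a questionnaire inquiring about the number of patients with uncontrolled HTN who received medication treatment and lifestyle counseling". The Analysis for Aim 3 agrees: "Adoption at 12 months will be assessed using questionnaires completed by nurses". Section 6 also requires every nurse to keep an attendance log of patient visits.

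**Who reports, and under what conditions.** Section 4 has sites told their group by telephone. In the PF arm, the first onsite meeting has the nurses "review the TASSH protocol, and set targets for the PHCs". Facilitators then coach and observe them, and Section 1 lists performance feedback as part of the intervention. Group B nurses are trained in the 5As and referral but get no facilitation.

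**Source at 24 months.** Section 6 defines sustainability as maintenance of adoption and says: "Sustainability will be assessed with a quantitative rate similar to adoption (as defined above) and qualitatively". The Analysis for Aim 3 says "For sustainability, the analysis will be repeated as described above but will be evaluated at 24 months instead of 12 months", but then that "sustainability at 24 months will be assessed with site interviews and site visits".

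**Composite.** The opening of Statistical Considerations takes the within-clinic proportion diagnosed, counselled and treated at 12 months, and the proportion screened, counselled and treated at 24 months. Section 6 defines adoption as a proportion, yet words its first measure as "the number of hypertensive patients diagnosed by" the nurses.

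**Records.** The Section 9 timeline has a post-implementation row, "Extract utilization and referral data from health record", that is tied to no outcome.

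**The concern.** There are two separate problems.

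The first is who supplies the data. The people whose behaviour is being measured report it themselves and know their arm. Only one arm is coached towards targets on the very activities being counted. A difference in how the arms report would be indistinguishable from a PF effect on adoption, which is part of Hypothesis 2 and the core of Aim 3. Adoption also enters the Aim 4 path model, including its link to SBP reduction, so the problem carries forward. The primary SBP outcome does not use the questionnaires.

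The second is consistency over time. An outcome defined as maintenance needs the same measurement at each time point. If the 24-month value comes from interviews and visits, and counts screening instead of diagnosis, a fall or a plateau may reflect the instrument and not the clinics. The Aim 3 model is fitted from baseline to follow-up with a group-by-time term, so mixed instruments could enter that model too. No source is named for the baseline adoption value.

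**Working it through.** **1. Is any check of the nurse counts specified?** The candidates in the protocol are:
- Attendance log (Section 6): required of all nurses, but kept by the reporters themselves and described only as a log of visits.
- Research coordinator (Section 5, Follow-up Study Visits): collects secondary outcomes in general terms. This does not replace the questionnaire, and Section 4 says coordinators cannot be blinded.
- REDCap entry (Data collection, handling, record keeping): done by the HIV nurses.
- Electronic capture of referrals (Section 4): described under compliance for Group A and not stated for Group B.
- Record extraction (Section 9): utilization and referral data. Diagnosis, counselling and starting treatment are not mentioned.

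None is specified as a check on the counts.

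**2. The statements on measurement, side by side.**

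| | 12 months | 24 months |
|---|---|---|
| Section 6 | nurse questionnaire | rate similar to adoption, plus interviews |
| Analysis for Aim 3, source | nurse questionnaire | interviews and site visits |
| Analysis for Aim 3, model | group, time, group by time | same model repeated |
| Statistical Considerations, composite | diagnosed, counselled, treated | screened, counselled, treated |

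The 24-month source differs between two sections, and the first component differs between time points.

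**3. Illustration of differential reporting.** The protocol gives no adoption rate, variance or ICC, so there is no stated figure to reproduce. The only design input is 15 clinics per arm. Assumptions: no true arm difference; PF clinics over-report by b more than control clinics; between-clinic SD of the clinic proportion of 0.15, 0.20 or 0.25; two-sided 5% t-test on clinic proportions.

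SE = SD × √(2/15), which gives 0.0548, 0.0730 and 0.0913. The noncentrality is b/SE with 28 df, and the critical value is 2.048. For example, b = 0.10 and SD = 0.20 gives 0.10/0.0730 = 1.37, and a rejection probability of 0.26.

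| b (points) | SD 0.15 | SD 0.20 | SD 0.25 |
|---|---|---|---|
| 2.5 | 7% | 6% | 6% |
| 5 | 14% | 10% | 8% |
| 10 | 42% | 26% | 18% |
| 15 | 75% | 51% | 35% |

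**4. A second model.** Let PF nurses wrongly report a share r of non-recipients as recipients, with true rate p in both arms. The false difference is r(1 − p). Use 15 × 32 = 480 patients per arm and effective n = 480/(1 + 31 × ICC), which is 366, 188 and 117 at assumed ICCs of 0.01, 0.05 and 0.10. With p = 0.50:
- r = 10% gives 5 points, and a significant result favouring PF with probability 27%, 16% and 12%.
- r = 20% gives 10 points, and 78%, 50% and 34%.

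**5. Illustration of an instrument change.** Suppose the 12-month questionnaire over-reports by r, the 24-month source does not, and the true rate is constant. The apparent change is −r(1 − p). For r of 5 to 20% and p of 0.30 to 0.70, this runs from −0.05 × 0.30 = −1.5 points to −0.20 × 0.70 = −14 points.

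**The case against.** The strongest reply is that no bias has been shown. Quarterly onsite observation by facilitators could restrain over-reporting as easily as encourage it, and facilitators leave after 12 months, so any asymmetry should weaken by 24 months. This stands: direction and size are both unknown. It does not supply a check.

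A reader might infer four stronger conclusions that the documents do not support:

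- *That 12 and 24 months are not comparable.* Section 6 provides for a quantitative rate similar to adoption, and Aim 3 repeats the same model. Only one sentence in Aim 3 points to interviews and visits. The source is contradictory, not settled. No 12-to-24-month test is specified either.
- *That a changed source biases the 24-month arm comparison.* Both arms would share it, so it does not do so by itself.
- *That the composite tracks clinic size because its first measure is a count.* Statistical Considerations analyses a within-clinic proportion, and about 32 patients are recruited per clinic. The count is one item that conflicts with the proportion stated elsewhere.
- *That the trial already holds better data.* The logs and REDCap entries come from the same nurses, referral capture is described only for Group A, and the extraction is not shown to hold the three components.

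It is also fair that the false-positive figures rest on assumed inputs and on a t-test of clinic proportions, not on the planned three-level model.

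**Conclusion.** The point holds in two parts. First, adoption at 12 months depends on self-report by nurses who know their arm, with targets, coaching and feedback in one arm only and no stated verification. Differential reporting could therefore affect the arm comparison by an unknown amount in either direction. Second, the 24-month source and the first component of the composite are stated inconsistently. If the interviews-and-visits sentence is followed, a change from baseline or from 12 months may be a change of instrument.

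The size is illustrative. Under the assumed SDs of 0.15 to 0.25, the false-positive chance is about 6 to 7% for 2.5 points of differential over-reporting, 8 to 14% for 5, 18 to 42% for 10 and 35 to 75% for 15. The top of that range is an extreme corner and should not be quoted alone. The issue should be corrected before analysis because it touches Aims 3 and 4. It does not threaten the primary SBP result.

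**What to change.** Amend Section 6, the opening of Statistical Considerations and the Analysis for Aim 3 so that they agree:

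1. Use one quantitative source and one composite at baseline, 12 and 24 months in both arms.
2. Use the same three components each time, each as a proportion with a stated denominator, and choose either diagnosis or screening as the first.
3. Keep the 24-month interviews and site visits as qualitative support only.
4. Cross-check questionnaire counts against the attendance logs required of all nurses and, where it holds the relevant items, the planned record extraction. Report agreement by arm.
5. Do not use the electronic referral capture for this unless it is collected in both arms.

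The cost is wording changes plus modest extra data handling at each time point. It would be more if the extraction had to be widened beyond utilization and referral. The logs are kept by the nurses, so the check reduces reporting bias but does not remove it.
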